## **Dissemination of Results and Publication Policy**

The results will be first reported via the National Centre of Research and Development, Poland, to the Ministry of National Defence, Poland. The Ministry will decide whether to implement the ORTHO-LBNP system into the selection process of candidates for military pilots.

The publications will be prepared under the leadership of the PI. The PI decides on the author lists. Only persons who gave the conception of the prototype system, modelled the tilt table and LBNP chamber, designed and constructed the prototype system, coordinated certification procedures, programmed the tilt and LBNP profiles, designed the experimental protocol, coordinated the pilot study, processed data for analysis, analysed and verified data, and interpreted the results, can be included on the author lists. The person who contributes the most to the preparation of the manuscript will be its first author. If the PI is not the author of the largest contribution, he will be acknowledged as the last author of the article.

All authors will review the manuscripts and accept their final version.

## **Duration of the Project**

Duration of the project is December 2012 - February 2018.

Realisation of the research scenarios is scheduled for February 2017 - February 2018.

## **Problems Anticipated**

A comprehensive risk analysis has been developed for the project, identifying the following hazard areas:

1. Energy threats (39 risks).
2. Biological and chemical hazards (7 risks).
3. Environmental hazards (8 risks).
4. Risks arising from the release of energy, substances and the selection of subassemblies (8 risks).
5. Risks associated with the use of the product (27 risks).
6. Risks related to usability (16 risks).
7. Hazards of damage and malfunction (11 risks).
8. Risks associated with embedded software (8 risks).
9. Risks associated with SOUP software (2 risks).
10. Risks associated with PC software (7 risks).

Each of the identified risks can be minimized to an acceptable level. None of them is a risk determined as certain.

The risk analysis is not part of this document due to its extensiveness.

## Project Management

The project is managed in accordance with the PRINCE2 methodology. The PI manages the Team Leaders who come from the member institutions implementing the project listed in the General Information section. The PI shall consult and report the results of the project to the Steering Committee, in which each of the member institutions has one representative.

## Ethics

Tilt and LBNP test are recognised as relatively safe interventions, however ventricular arrhythmias or asystole can appear. For decades, research works involving military pilots have been conducted at MIAM. Most of these studies have been interfered with the cardiovascular system to a greater or lesser extent. Therefore, the institute has qualified personnel to conduct such a research, an advanced rescue team and the ethics committee that deals with studies in real or simulated conditions.

Potential subjects will be informed on the study at least 30 days before the planned study. Those who are initially interested in the study participation will receive a copy of the research protocol for acquainting. They should decide at least 15 days before the beginning of the planned study and inform the PI or a study coordinator appointed by the PI. Just before the study, the subjects will receive two copies of the informed consent form to acquaint and sign. One of the signed copies is for the subject and the other is for the sponsor.

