**Fig. 6. Tilt and LBNP profiles in 24-min Scenario I.**

### Scenario II

Scenario II will be composed of seven phases, shown in Fig. 7, which can be characterised as: (1) 120-s check before the stimuli, (2) 75°-HUT (45°/s) for 60 s after a 3-s reversing of the gravity vector (-30°), (3) 180-second phase of rest between stimuli, (4) LBNP decreases linearly by -20 mmHg/s to -100 mmHg, and then this value is sustained for 60 s, (5) 180-second phase of rest between stimuli, (6) push-pull, i.e.,  $3 \times 75^\circ$ -HUT (45°/s) preceded by -30°-HDT (45°/s) and accompanied by an exposure to an LBNP of -60 mmHg decreased linearly by -20 mmHg/s, and then this value is sustained for 30 s during HUT, and (7) 120-s check after the stimuli.

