## Safety Considerations

The subjects will be informed of possible presyncope symptoms that may occur during the tilt and/or LBNP exposure, with an emphasis on the prompt notification of any symptoms. Prior to the exposure, a shortened medical survey will be performed, including a subjective examination for possible contraindications to the exposure, and a physical examination, i.e., RR and HR measurements in sitting and standing positions. Once the subject is placed in the LBNP chamber, their resting ECG as well as SBP and DBP will be assessed.

Both tilt and LBNP tests are relatively safe, but complications in the form of ventricular arrhythmias or asystole are known. Therefore, at the time of the study, the presence of trained medical personnel, consisting of a physician and paramedic, shall be provided. The following rescue equipment will be available:

1. Ambu self-inflating bag with connector to supply oxygen.
2. Oxygen cylinder with reducer. Check the filling status before exposure!
3. Automatic defibrillator. Check the battery charge before exposure!
4. Anti-shock kit in accordance with the Executive Regulation of the Minister of Health of 24 September 2013 on the guaranteed benefits in the area of primary healthcare (Journal of Laws, 2013, item 1248) and Law of 6 September 2001 - Pharmaceutical Law (Journal of Laws, 45, 2008, item 271) with amendments. The detailed composition of the anti-shock kit is presented in **Appendix A** to this research protocol.

If presyncope syndromes are present, immediately stop the HUT and/or LBNP exposition and move the tilt table to the Trendelenburg position (tilt angle of  $-16^{\circ}$ ). There is a difference in the way of handling push-pull simulations. The procedure depends on the study phase. For  $+G_z$  exposures, i.e., HUT and/or LBNP, immediately stop the LBNP exposure (if used) and move the tilt table to the Trendelenburg position. In the event of any feeling of discomfort by the subject during  $-G_z$  exposures, i.e., HTD, the orthostatic exposition should be discontinued and returned to the horizontal position of the tilt table (tilt angle of  $0^{\circ}$ ).

In case of asystole or ventricular arrhythmias in the form of ventricular tachycardia or ventricular fibrillation, the resuscitation procedure should be implemented in accordance with the adult advanced life support (ALC) algorithm:

1. Check whether the victim reacts, whether breathing or not, or does not have single sighs.

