## Expected Outcomes of the Study

During the implementation of both research scenarios, all signals/parameters that can be acquired by the medical monitoring subsystem will be recorded. However, in scenario I the main emphasis will be placed on the analysis of basic physiological parameters, i.e., HR, inter-beat interval (IBI), SBP, DBP, mean arterial pressure (MAP), stroke volume (SV), cardiac output (CO), left ventricular ejection time (LVET), rate pressure product (RPP), and total peripheral resistance (TPR), calculated using the ECG and CNAP signals. The latest literature shows that the analysis of basic physiological parameters, e.g., heart rhythm and blood pressure, enables for predicting orthostatic hypotension [23] and reveals precursory signs of syncope [24]. Our intention is to verify the behaviour of a group of cadets experiencing accelerations on a regular basis who are subject to tests in a device of a novel design. We expect that a stronger stimulus will cause greater changes in the values of the analysed physiological parameters. Among the stimuli used, the strongest one should be HUT accompanied by LBNP. The analysis should indicate these physiological parameters that should be taken into account in the development of an orthostatic tolerance index (OTI).

The results of scenario II will be focused not only on the impact of the stimuli, but will also be analysed in terms of the distinguishing of subjects with different level of flight experience and quantifying an examined person's propensity to endure gravitational stimuli. Both analysis of basic physiological parameters as well as analysis of indices determining the level of oxygenation of brain areas acquired with the in-house-designed NIRS module will be

performed. It is expected that greater changes in brain oxygenation indices will be seen in the subjects without flight experience than in active pilots that have undergone a training improving their G-tolerance.

We anticipate that new indicators will be proposed to enable an objective assessment of the predispositions to pursue a military pilot career. Finally, this should make the selection procedures in military aviation easier.

At least two manuscripts, one containing the results of scenario I, the other containing the results of scenario II, will be submitted for publication.

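### Every interested person receives the full protocol, which states the expected pilot-student difference in brain oxygenation, so expectation can enter the Scenario II comparison

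*Combined protocol and SAP*

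**What the plan says.** Under Ethics, potential subjects hear of the study at least 30 days ahead. Of these, "Those who are initially interested in the study participation will receive a copy of the research protocol for acquainting". Then: "They should decide at least 15 days before the beginning of the planned study". The consent form follows only just before the session. No abridged version of the protocol is mentioned there.

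The protocol they receive contains:
- the expected group difference, under Expected Outcomes of the Study: "It is expected that greater changes in brain oxygenation indices will be seen in the subjects without flight experience than in active pilots";
- the expected ranking of stimuli, in the same section: "Among the stimuli used, the strongest one should be HUT accompanied by LBNP";
- the order and timing of the stimuli, under Research scenarios. Scenario II, for example, opens with "120-s check before the stimuli, (2) 75°-HUT (45°/s) for 60 s";
- the role of each group, under Study Design: up to 15 pilots or senior cadets, and up to 15 aviation high-school students as the reference group.

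The Statistical Analysis Plan describes changes relative to phase 1 and then relates the parameters of the two groups to each other.

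**The concern.** The pilot-student comparison is meant to support objective indicators of suitability for a flying career, so a difference between the groups will be read as physiology. Subjects cannot be blinded to their own flight experience. They can, however, be left unaware of what the investigators expect of their group, and the plan tells them.

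Some of the measured quantities may respond to a subject's state. Arousal before the first stimulus can alter the phase 1 reference. The protocol itself notes, in explaining the optional saddle, that leg muscle tension pushes blood toward the upper body. If the two groups react differently to what they have read, part of the observed difference reflects that reaction and not flight experience. The conduct rules closest to this point are closed eyes and no conversation during the test, and neither undoes prior knowledge. The plan describes no measure of expectation and no signal processing blind to group.

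**Working it through.** The plan gives no significance level, effect size, SD or power, so there is no figure of its own to reproduce. The check has three parts.

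**1. Which outcomes have a disclosed direction.** The Statistical Analysis Plan lists 10 ECG/CNAP parameters, 4 impedance parameters and 3 NIRS parameters for Scenario II: 10 + 4 + 3 = 17. The stated group expectation concerns brain oxygenation, that is, the 3 NIRS parameters. No group direction is stated for the other 14.

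**2. How a reaction would pass into the contrast.** For group g (S = students, P = pilots), let d_g be the true change from phase 1, a_g the shift caused by expectation in phase 1, and s_g the shift during the stimulus.
- Observed change = d_g + s_g − a_g.
- Observed contrast = (d_S − d_P) + [(s_S − s_P) − (a_S − a_P)].

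If both groups react alike, the bracket is zero. The contrast is then unaffected, although each change from phase 1 still carries s − a. If only phase 1 arousal differs and students are the more aroused, the bracket is −(a_S − a_P). For a parameter that rises under the stimulus, such as heart rate, this shrinks the students' change. The sign of any bias is therefore not fixed.

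**3. Scale, under assumption.** Inputs: 15 per group (the ceilings in Study Design), two-sided 5% (assumed), no true difference, and a differential shift of b SD (assumed; the documents give no basis for any value). For a two-sample t-test on 28 degrees of freedom, the noncentrality is b / √(2/15) = b / 0.365. The chance of a significant result is the probability that the noncentral t falls outside the two critical values.

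| b (SD) | Noncentrality | Chance of significance |
|---|---|---|
| 0.10 | 0.27 | 0.058 |
| 0.25 | 0.68 | 0.101 |
| 0.50 | 1.37 | 0.262 |
| 0.75 | 2.05 | 0.509 |
| 1.00 | 2.74 | 0.753 |

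The nominal rate is 0.05. The figures apply to each affected parameter. The plan expects to use nonparametric tests, so they indicate scale only.

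**The case against.** Giving healthy volunteers the whole protocol is a defensible act of openness when the procedure carries a known risk of arrhythmia or asystole. Both groups read the same text, so the contrast is biased only if they react differently. The assumed shift would produce the same percentages for any confounder one cared to imagine. The groups are not randomised, and that problem is probably larger and would remain. All of this stands. It limits the claim to an open and avoidable route for bias, and it is why the remedy must withhold no risk information.

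A reader might infer more, and the documents do not support it:
- *That the plan discloses a direction for every outcome.* It does so for brain oxygenation only.
- *That the hypothesis fulfils itself.* As shown above, phase 1 arousal can reduce a change as well as enlarge one.
- *That expectation could never be separated afterwards.* Skin conductance, EMG and capnography are among the monitoring modules, and all obtainable signals are to be recorded. They are not in the analysis plan and the EMG site is not given, so separation is possible but not assured.
- *That stopping rests on subjects' reports alone, which career interest might suppress.* Safety Considerations does inform subjects "with an emphasis on the prompt notification of any symptoms". But the physician also watches the ECG, heart rate and blood pressure and can have the test interrupted. Nothing says that an individual's result affects that person's career. An information sheet would in any case still state the purpose and the use of data.

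**Conclusion.** The point holds in a limited form. The plan hands each interested person the expected pilot-student difference in brain oxygenation before the session, and expectation can therefore enter the Scenario II comparison. Size and direction are unknown. The 10% to 26% range rests wholly on an assumed differential shift of 0.25 to 0.5 SD, 15 per group and a two-sided 5% t-test. Scenario I has no pilot-student contrast; there, and for any reaction common to both groups in Scenario II, what is exposed is the phase 1 reference and the comparison of phases.

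One might also conclude that subjects should not know the order of the stimuli. That does not follow: some knowledge of what is coming belongs to informed consent, and the gain from withholding it is debatable. The clearly avoidable part is the statement of expected results. This is a cheap improvement to an exploratory pilot study, not a flaw that invalidates it.

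**What to change.** In the Ethics section, replace the copy of the protocol with one participant information sheet, identical for pilots and students. It should cover the purpose, the kinds, order and limits of the stimuli, the duration, all risks, the right to stop and the use of data. It should leave out the expected group difference and the expected ranking of stimuli. Offer the full protocol after the subject's own session.

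Optionally, compare phase 1 skin conductance, EMG and capnography between the groups as a check on arousal, bracing and breathing. These signals are already to be recorded.

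State in the report that the groups are not randomised and that differences other than flight experience may explain a contrast. The sheet does not remove that confounding.

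The cost is a short document, an ethics notification and later access to the full protocol. No risk information is withheld and nothing in the sessions changes.

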## Informed Consent Forms

A copy of the informed consent form in English is included as **Appendix C**.

## Budget

The project is supported by the resources of the National Centre of Research and Development (NCRD), Poland, within the framework of the Program for National Defence and Security.

Information on the budget level is not available due to a military character of the project.

## Other support for the Project

No other funds.

## Links to other projects

ID	Project No.	Title	Source of funding	Duration	Publications
1.	03/WNiI/2007/IWSZ	Improvement of examinations in real flight conditions of physiological and psychological parameters in cadets and pilots retrained on new types of aircraft for the assessment of environment and training progress	Ministry of National Defence, Poland	2007–2013	1. DOI: 10.3357/AMHP.4087.2015

**Financing and Insurance**

All diagnostic surveys and pilot studies performed at MIAM are insured.

## Appendix A

### List of medicinal products being part of the anti-shock kit, which may be given by a physician

1. Aminophyllinum 0,25 g - 10 amp. a 10 ml.
2. Antazolini hydrochloridum 50 mg/ml - 5 amp. a 2 ml.
3. Aqua pro inj. - 5 amp. a 5 ml.
4. Atropini sulfas 1 mg - 10 amp. a 1 ml.
5. Calcii chloridum or Calcii gluconas - solutions 10% - 10 amp. a 10 ml.
6. Clonazepamum a 1 mg - 10 amp. a 1 ml.
7. Dopamini hydrochloridum 4% - 10 amp. a 5 ml.
8. Epinephrinum a 1 mg - 10 amp. a 1 ml.
9. Furosemidum 20 mg - 5 amp. a 2 ml.
10. Glucosum 40% 2 - 10 amp. a 10 ml.
11. Glyceroli trinitras aerosol - 1 pack.
12. Hydrocortisonum 250 mg - 5 phial a 250 mg + 5 amp. diss. a 2 ml or Methylprednizolonum 40 mg - 1 phial a 40 mg + 1 amp. diss., Methylprednizolonum 125 mg - 1 phial a 125 mg + 1 amp. diss., Methylprednizolonum 250 mg - 1 phial a 250 mg + 1 amp. diss., Methylprednizolonum 500 mg - 1 phial a 500 mg + 1 amp. diss., Methylprednizolonum 1000 mg - 1 phial a 1000 mg + 1 amp. diss.
13. Lidocaini hydrochloridum 2 % - 10 amp. a 2 ml.
14. Metamizolum natricum 2,5 g - 5 amp. a 5 ml.
15. Metoprololi tartas 1 mg/ml - 5 amp. a 5 ml.
16. Morphini sulfas 20 mg/1 ml - 2 amp. a 1 ml.
17. Naloxoni hydrochloridum 0,4 mg/1 ml - 10 amp. a 1 ml.
18. Natrii chloridum 0.9% - 10 amp. a 10 ml.
19. Natrii hydrocarbonas 8.4-% solution for intravenous injection - 5 amp. a 20 ml.
20. Salbutamoli sulfas aerosol 100 mcg/dose - 1 pack.
21. Salbutamoli sulfas a 0,5 mg - 10 amp. a 1 ml.
22. Thiethylperazini dimaleas a 6,5 mg/ml - 5 amp. a 2 ml.
23. Tramadoli hydrochloridum 50 mg/ml - 5 amp. a 2 ml.
24. Verapamili hydrochloridum 2,5 mg/ml - 5 amp. a 2 ml.

#### Infusion fluids:

1. Calcii chloridum + Kalii chloridum + Natrii chloridum (Ringer's fluid) - 1 pack a 250 ml.
2. Glucosum 5 % - 1 pack a 500 ml.
3. Glucosum 10 % - 1 pack a 500 ml.
4. Mannitolum 20 % - 1 pack a 250 ml.
5. Natrii chloridum 0,9 % - 2 pack a 500 ml.

## List of medicinal products being part of the anti-shock kit, which may be given by a paramedic

1. Antazolini hydrochloridum 50 mg/ml - 5 amp. a 2 ml.
2. Aqua pro inj. - 5 amp. a 5 ml.
3. Atropini sulfas 1 mg - 10 amp. a 1 ml.
4. Calcii chloridum or Calcii gluconas - solutions 10% - 10 amp. a 10 ml.
5. Hydrocortisonum 250 mg - 5 phial a 250 mg + 5 amp. diss. a 2 ml or Methylprednizolonum 40 mg - 1 phial a 40 mg + 1 amp. diss., Methylprednizolonum 125 mg - 1 phial a 125 mg + 1 amp. diss., Methylprednizolonum 250 mg - 1 phial a 250 mg + 1 amp. diss., Methylprednizolonum 500 mg - 1 phial a 500 mg + 1 amp. diss., Methylprednizolonum 1000 mg - 1 phial a 1000 mg + 1 amp. diss.
6. Epinephrinum a 1 mg - 10 amp. a 1 ml.
7. Glucosum 20% - 10 amp. a 10 ml.
8. Natrii chloridum 0.9% - 10 amp. a 10 ml.

### Infusion fluids:

1. Calcii chloridum + Kalii chloridum + Natrii chloridum (Ringer's fluid) - 1 pack a 250 ml.
2. Glucosum 5 % - 1 pack a 500 ml.
3. Glucosum 10 % - 1 pack a 500 ml.
4. Natrii chloridum 0,9 % - 2 pack a 500 ml.

Appendix B

(Copies of certificates)
